#### 4.4 Software

All report outputs will be produced using SAS® version 9.4 or a later version in a secure and validated environment.

#### 4.5 Study Subjects

##### 4.5.1 Disposition of Subjects

A clear accounting of the disposition of all subjects who enter the study will be provided, from screening to study completion.

Subject disposition will be summarized by treatment and overall for:

- Number of subjects screened
- Number of subjects with screen failure
- Number of subjects randomized
- Number and percentage of subjects received at least one dose of study drug
- Number and percentage of subjects discontinued from study drug and primary reason for premature discontinuation
- Number and percentage of subjects discontinued from study and primary reason for premature discontinuation

By-subject listings of disposition details will also be provided.

##### 4.5.2 Protocol Deviations

Protocol deviations will be classified as “major” or “minor” on ongoing basis by the clinical study team and sponsor.

Major protocol deviations are defined as those deviations from the protocol likely to have an impact on the subject’s right, safety, well-being, and/or the validity of the data for analysis. Minor protocol deviations include all deviations from the protocol excluding the major protocol deviations.

Major protocol deviations and any action to be taken regarding the exclusion of subjects or affected data from specific analyses are defined in the project-specific Protocol Deviation Specification.

The number and percentage of subjects with a major protocol deviation on Full Analysis Set by treatment and overall will be summarized. By-subject listing of all protocol deviations will also be provided.

#### 4.6 Analysis Populations

##### Randomised Set

The Randomised Set consists all subjects who are randomized to treatment.

#### Full Analysis Set (FAS)

The Full Analysis Set (FAS) consists of randomized subjects who received at least 1 dose of study treatment and at least one primary endpoint datum collected during the treatment period. These subjects are grouped based on the treatment group to which were randomized. If a subject is allocated the incorrect study treatment as per the study randomization list, subjects will be summarized and analyzed 'as randomized' i.e. by randomized treatment group. The efficacy summaries and analyses will be based on the Full Analysis Set (FAS), which is based upon the Intention-to-Treat principle.

#### Per Protocol Set (PPS)

The Per Protocol Set (PPS) is defined as a subgroup of patients in FAS without major protocol deviations. A sensitivity analysis will be performed on the Per Protocol Set to assess the robustness of the study conclusions to the choice of analysis set for the primary efficacy variable.

#### Safety Set (SS)

The Safety Set (SS) is defined as all randomly assigned patients who received at least 1 dose of study treatment. These patients will be categorized according to the treatment they actually received. If a subject is allocated the incorrect study treatment as per the study randomization list, subjects will be summarized and analyzed 'as treated' i.e. by allocated treatment group. The safety summaries and analyses will be based on the Safety Set.

#### Pharmacokinetic Set (PKS)

The Pharmacokinetic Set (PKS) consists of all randomly assigned patients from whom at least 1 post-dose PK blood sample was collected. Pharmacodynamic (PD) and/or PK relationships will be explored in a separate analysis plan and report.

An analysis population classification meeting will be arranged to discuss the outputs and to decide which subjects and/or subject data will be excluded from certain analyses. Decisions made regarding the exclusion of subjects and/or subject data from analyses will be made prior to unblinding and will be documented and approved by Suzhou Connect Biopharmaceutical Ltd.

The number and percentage of subjects in each analysis set by treatment group and overall will be summarized on Randomised Set. By-subject listing of analysis population assignment will also be provided.

#### **4.7 Demographic and Other Baseline Characteristics**

Age at baseline (years), gender, race, ethnicity, geographic region, height (cm) at Baseline, weight (kg) at Baseline, presence of comorbid asthma at Baseline, type 2 inflammation at Baseline marked by Baseline blood eosinophil count  $\geq 300$  cells/ $\mu$ L, endoscopic NPS at Baseline, average daily NCS at Baseline week, LMK CT score at Baseline, NPIF at Baseline, and FEV1 at Baseline for asthma patients will be summarized on Full Analysis Set by treatment and overall.

By-subject listing of demographic and other baseline characteristics will also be provided.

## 4.8 Medical History

Medical history at screening will be coded using the Medical Dictionary for Regulatory Activities (MedDRA) Version 24.0 and summarized on Safety Set by treatment and overall using system organ class and preferred term. By-subject listing of medical history will also be provided.

## 4.9 Prior and Concomitant Medication

Medication start and stop dates will be compared to the date of first dose of study drug to allow medications to be classified as either Prior only, both Prior and Concomitant, or Concomitant only as defined in [4.2](#). Medications starting after the completion/withdrawal date will not be classified or summarized.

Incomplete start and end date of the medications will be imputed as described in [Error! Reference source not found.](#)

Concomitant medications and Prior and Concomitant medications will be coded using the World Health Organization Drug (WHODrug) Global March 2021 B3 and summarized on Safety [Set](#) by treatment and overall. Subjects with more than one medication in a given ATC level and preferred term will be counted only once.

By-subject listings of prior and concomitant medications will also be provided.

## 4.10 Treatment Compliance

Treatment compliance (%) is calculated as described in [4.2](#). A summary of the treatment compliance at each visit and overall treatment period will be provided on Safety [Set](#) by treatment and overall. By-subject listing of treatment compliance will also be provided.

## 4.11 Efficacy Evaluation

### 4.11.1 Statistical Analysis and Data Conventions

Unless otherwise specified, all statistical tests will be interpreted at a 2-sided significance level of 0.05 and all CIs at a 2-sided level of 95%. The overall type I error rate is 0.05 (two-sided) for the primary and secondary efficacy hypotheses.

#### 4.11.1.1 Adjustments for Covariates

The primary and secondary efficacy analysis will be adjusted for the following baseline covariates:

1. Presence of comorbid asthma (stratification factor)
2. Endoscopic NPS at baseline (baseline measure of the primary efficacy variable)

For each covariate, a statistical test for the presence of a treatment-by-covariate interaction will be performed, by including the interaction term in the primary analysis model. If any of the treatment-by-covariate interactions are found to be statistically significant at the 5% level ( $p < 0.05$ ), subgroup analyses will be performed to further explore the nature of the interaction. In such cases, conclusions based on the primary analysis (no interaction) will be interpreted with caution.

#### 4.11.1.2 Handling of Missing Efficacy Data

For primary analysis, MMRM will be performed to mitigate the impact of missing data. This approach assumes that missing observations are missing-at-random (missingness is related to

observed data) during the study and borrows information from patients in the same treatment arm taking into account both the missingness of data and the correlation of the repeated measurements. All secondary and exploratory efficacy analyses as well as safety analyses will be conducted without imputation of missing values.

To assess the robustness of the study conclusions to the choice of imputation method, the sensitivity analyses will be performed for the primary variable (see [4.11.3](#)).

#### **4.11.1.3      Multiple Comparisons/Multiplicity**

The primary analysis will compare the CBP-201 Q2W 300 mg group to the placebo group using a two-sided test at the alpha=0.05 level of significance. “Study success” is defined as a statistically significant result for both of the co-primary endpoints. If both of the co-primary endpoints are statistically significant (p-value<0.05) then the same model as described [0](#) will be used for the key secondary analysis to compare the CBP-201 Q4W 300 mg group to placebo group using a two-sided test at the alpha=0.05 level of significance.

The definition of study success and use of a fixed sequence testing procedure for the primary analyses controls the overall level of significance. Hence there is no formal control for multiplicity planned.

#### **4.11.1.4      Interim Analyses**

No interim analyses are planned.

#### **4.11.1.5      Examination of Subgroups**

Baseline characteristics, all efficacy (including primary, secondary, and exploratory), safety, and PK/PD endpoints will be examined for the following subgroups:

- Ethnicity: Asian vs Non-Asian
- Country: Chinese vs Non-Chinese

Summaries of baseline characteristics, efficacy and safety endpoints by treatment group and subgroup will be produced. No sensitivity analysis will be performed within subgroup. No formal statistical analysis will be performed within subgroup.

Details of PK [subgroup](#) analysis will be provided by a separate PK analysis plan.

### **4.11.2 Co-primary Efficacy Analysis**

The co-primary endpoints for the assessment of efficacy are the change from Baseline in endoscopic nasal polyp score (NPS) at Week 24 and average daily nasal congestion score (NCS). Endoscopic NPS and average daily NCS at Week 24 will be summarized by treatment group in terms of absolute values and changes from baseline.

#### **4.11.2.1      Endoscopic Nasal Polyp Score (NPS)**

Nasal Polyps Score (NPS) is assessed by central video recordings of nasal endoscopy. The score (NPS) is the sum of left and right nostril scores, as evaluated by means of nasal endoscopy. NPS is graded based on polyp size as described below:

Polyp Score	Polyp Size
0	No polyps

1	Small polyps in the middle meatus not reaching below the inferior border of the middle turbinate
2	Polyps reaching below the lower border of the middle turbinate
3	Large polyps reaching the lower border of the interior turbinate or polyps medial to the middle turbinate
4	Large polyps causing complete obstruction of the inferior nasal cavity

The effect of treatment in terms of the change from Baseline to Week 24 in endoscopic NPS will be analyzed using Mixed-effect Model for Repeated Measures (MMRM).

The model will include treatment, presence of comorbid asthma, visit, treatment-by-visit interaction as categorical covariates, and endoscopic NPS at baseline as continuous covariates. Patient will be included as a random effect. An unstructured (UN) covariance matrix will be used to model the within-subject correlation. If this model fails to converge, then Akaike's Information Criterion (AIC) will be used to select the best covariance matrix among compound symmetry (CS), first-order autoregressive (AR(1)), and Toeplitz (TOEP). The treatment effect will be estimated using the difference between the treatments least squares means (adjusted means). The 95% confidence interval for the difference between the treatments least squares means and the p-value from the hypothesis test of no difference between the treatment groups will be also presented.

The sample SAS code for MMRM:

```
proc mixed data= data;
  class subjid cmabl trt01pn(ref='1') avisitn;
  model chg = trt01pn cmabl trt01pn*avisitn npsbl*avisitn / ddfm=kr;
  repeated avisitn / subject=subjid type=UN;
  lsmeans trt01pn*avisit / pdiff cl alpha=0.05;
  ods output lsmeans=lsmeans diff=diffs;
run;
```

A plot showing the LS mean of endoscopic NPS  $\pm$  SE bar over time within each treatment group will be provided.

Sensitivity analyses to investigate the impact of the choice of method for handling missing data and the choice of analysis set will be performed as described in [4.11.3](#).

By-subject listing of the primary efficacy data will also be provided.

#### 4.11.2.2 Average Daily Nasal Congestion Score (NCS)

Daily Nasal Congestion Score (NCS) will be assessed by the patient through a patient diary from Visit 1 throughout the study by using a 0 to 3 categorical scale for severity of symptoms from none to severe over the past 24 hours.

Question: How would you rate nasal congestion over the last 24 hours?	
0	None
1	Minor
2	Moderate
3	Severe

Weekly mean of daily nasal congestion score will be calculated as sum of non-missing daily nasal congestion score divided by number of days with non-missing daily nasal congestion score using analysis window (Table ). The effect of treatment in terms of the change from Baseline week (i.e. average of 7 days prior to the baseline visit) to Week 24 (i.e. average of 7 days prior to the Week 24 visit) in average daily NCS will be also analyzed using Mixed-effect Model for Repeated Measures (MMRM).

The model will include treatment, presence of comorbid asthma, visit, treatment-by-visit interaction as categorical covariates, and average daily NCS at baseline as continuous covariates. Patient will be included as a random effect. An unstructured (UN) covariance matrix will be used to model the within-subject correlation. If this model fails to converge, then Akaike's Information Criterion (AIC) will be used to select the best covariance matrix among compound symmetry (CS), first-order autoregressive (AR(1)), and Toeplitz (TOEP). The treatment effect will be estimated using the difference between the treatments least squares means (adjusted means). The 95% confidence interval for the difference between the treatments least squares means and the p-value from the hypothesis test of no difference between the treatment groups will be also presented.

The sample SAS code for MMRM:

```
proc mixed data= data;
  class subjid cmabl trt01pn(ref='1') avisitn;
  model chg = trt01pn cmabl trt01pn*avisitn ncsbl*avisitn / ddfm=kr;
  repeated avisitn / subject=subjid type=UN;
  lsmeans trt01pn*avisit / pdiff cl alpha=0.05;
  ods output lsmeans=lsmeans diff=diffs;
run;
```

In addition to primary efficacy analysis summary, weekly mean of daily nasal congestion score will be summarized using descriptive statistics by treatment and overall.

A plot showing the LS mean of average daily NCS  $\pm$  SE bar over time within each treatment group will be provided.

Sensitivity analyses to investigate the impact of the choice of method for handling missing data and the choice of analysis set will be performed as described in 4.11.3.

By-subject listing of the primary efficacy data will also be provided.

#### 4.11.3 Sensitivity Analysis

##### 4.11.3.1 Sensitivity Analysis using PMM-MI

To assess the robustness of the study conclusions to the choice of imputation method, the sensitivity analyses will be performed for the primary variable using control-based Pattern Mixture Model Multiple Imputation (PMM-MI) under the missing not at random (MNAR) assumption, which assumes the missingness depends on the unobserved study data and cannot be predicted solely based on subject's observed data.

Control-based PMM-MI under MNAR involves following standard steps. Same procedures will be followed for average daily NCS.

##### Step 1. Assessing the pattern of missing data

To investigate the pattern of missing data, 'ods output misspattern' will be used in the MI procedure of the SAS system (PROC MI). The imputation method will be based on the observed pattern of

missing data and amount of missing data. The pattern of missing data will be assessed as monotone or arbitrary.

```
proc mi data=non_mono seed=xxx n impute=0;
  var trt01pn cmabl y0-y13; *y0=baseline, y13=week24;
  ods output misspattern=pattern;
run;
```

**Step 1-a.** Turning the arbitrary missing patterns to monotone missing patterns under MAR assumption

If a mixture of non-monotone and monotone missing patterns exist in the data with majority of monotone missing patterns, then the arbitrary missing patterns will be converted to monotone missing patterns under MAR assumption.

```
proc mi data=non_mono out=mono seed=xxx n impute=m;
  min=. . x x x x x x x x x x x x x x x x; *period (.) means no imputation needed;
  max=. . y y y y y y y y y y y y y y y y;
  var trt01pn cmabl y0 y1 y2 y3 y4 y5 y6 y7 y8 y9 y10 y11 y12 y13;
  memc chain=multiple impute=monotone;
run;
```

**Step 2.** Generation of imputed datasets using control-based pattern imputation

PROC MI will be used to generate  $m$  complete datasets. The selection of  $m$  depends on the required computing time but has been recommended varying from 5 to 100.

```
proc mi data=mono seed=xxx n impute=m outs=imputed;
  min=. . x x x x x x x x x x x x x x x x;
  max=. . y y y y y y y y y y y y y y y y;
  by _imputation_;
  class trt01pn cmabl;
  var cmabl y0 y1 y2 y3 y4 y5 y6 y7 y8 y9 y10 y11 y12 y13;
  monotone reg(/details);
  mnar model(y1 y2 y3 y4 y5 y6 y7 y8 y9 y10 y11 y12 y13/ modelobs=(trt01pn='1')); *only
  control group is used to derive the imputation model;
run;
```

**Step 2-a.** Convert datasets into long format in which CHG variable represents all change from baseline with different values of avisit.

**Step 3.** Conducting model-based analysis using each imputed dataset

The  $m$  complete datasets are analyzed using MMRM.

```
proc mixed data= imputed;
  by _imputation_;
  class subjid cmabl trt01pn(ref='1') avisitn;
  model chg = trt01pn cmabl trt01pn*avisitn ncsbl*avisitn / ddfm=kr;
  repeated avisitn / subject=subjid type=UN;
  lsmeans trt01pn*avisit / pdiff cl alpha=0.05;
  ods output lsmeans=lsmeans diff=diffs;
run;
```

**Step 4.** Pooling the results from the imputed  $m$  datasets for inference

The results from the m complete datasets are combined to produce inferential results.

```

proc sort data=lsmeans;
  by trt01pn avisitn_imputation_;
run;

proc mianalyze parms=lsmeans;
  modeleffects trt01pn*avisitn;
  ods output ParameterEstimates=lsm;
run;

proc sort data=diffs;
  by avisit_imputation_;
run;

proc mianalyze parms=diffs;
  modeleffects trt01pn*avisitn;
  ods output ParameterEstimates=dif;
run;

```

The Per Protocol Set analyses will be performed using the same imputation method as for the Full Analysis Set analyses.

#### 4.11.3.2 Sensitivity Analysis for Use of Rescue Medication

To assess the robustness of the study conclusions to use of rescue medication, another sensitivity analysis will be performed on the primary variable based on FAS.

Rescue medications are defined as below and will be reviewed by Parexel Medical Monitor:

- Nasal lavage with saline and/or systemic antibiotics (up to 2 weeks in case of acute infection)
- Short course oral CS (prednisone or prednisolone); use of oral/systemic CS for  $\leq 5$  consecutive days
- Treatment with oral/systemic steroids for  $> 5$  consecutive days
- Sino-nasal surgery for nasal polyps. Based on previous observations, at least 8 weeks of study drug treatment is recommended prior to resorting to surgery to allow an onset of the treatment effect. *Note: Patients receiving sino-nasal surgery during the study are required to discontinue study drug treatment as this is categorized as a treatment failure, although study assessments may continue.*

If patients used any rescue medication before Week 24, their assessments after the first use of rescue medication will be set to missing, and missing values at week 24 will be imputed using the subject's worst observed value over all previous time points including baseline value. Then the primary efficacy analysis using MMRM will be performed.

#### 4.11.4 Secondary Efficacy Analyses

The similar analyses to primary analysis will be applied to following secondary endpoints:

- Percentage of maxillary sinus volume occupied by disease on CT and Lund-Mackay Computed Tomography scores from patients enrolled at Study Centers that are approved and qualified to perform CT scans

- University of Pennsylvania Smell Identification Test (UPSIT)
- Visual Analogue Scale for Rhinosinusitis (VAS-RS) [Appendix ]
- Total Nasal Symptom Score (TNSS) [Appendix B – Total Nasal Symptom Score (TNSS)]
- 22-item Sinonasal Outcome Test (SNOT-22) [Appendix C – Sino-Nasal Outcome Test-22 QUESTIONNAIRE (SNOT-22)]
- Average daily anterior rhinorrhea score (from diary) \*
- Average daily posterior rhinorrhea score (from diary) \*
- Average daily loss of smell score (from diary) \*
- Daily subject-assessed Nasal Peak Inspiratory Flow (NPIF) \*

\*Weekly mean will be calculated as sum of non-missing endpoint divided by number of days with non-missing endpoint for daily assessments listed using analysis window (Table ). The effect of treatment in terms of the change from Baseline week (i.e. average of 7 days prior to the baseline visit) to Week 24 (i.e. average of 7 days prior to the Week 24 visit) will also be analyzed using MMRM.

Time to first rescue treatment (systemic corticosteroid for > 5 consecutive days) or having had surgery for nasal polyps during the 24-week Treatment Period will be analyzed using a Cox proportional hazard model. The model will be adjusted by treatment, presence of comorbid asthma, endoscopic NPS at Baseline, and average daily NCS at Baseline. Subjects who do not experience rescue treatment or surgery for nasal polyps during the 24-week Treatment Period will be censored at the earliest day among the component censoring times (end of study date, premature study discontinuation date, lost to follow-up date, date of death). Any events after 24-week Treatment Period will not be counted.

Estimated adjusted hazard ratios will be summarized with associated 95% CI and p-values.

The sample SAS code for the Cox proportional hazards model:

```
proc phreg data=datain;
  class subjid cmabl trt01pn(ref='1');
  model avisitn*event (1) = trt01pn cmabl / ties=efron rl=wald type3(wald);
    *0 is event, 1 is censored*;
  assess var = (trt01pn cmabl) ph / resample;
    *testing the proportionality assumption. Resample is specified to request the supreme tests
    of the null hypothesis that proportional hazards hold*;
  hazardratio trt01pn / diff=ref cl=wald alpha=0.05;
  ods output hazardratios=hazard;
run;
```

Time to first rescue treatment or having had surgery for nasal polyps during the 24-week Treatment Period will be displayed graphically for each treatment group using a Kaplan-Meier curve and analyzed using a log-rank test to compare the curves between the treatment groups.

The sample SAS code for the Kaplan-Meier Curve:

```
proc lifetest data=datain atrisk plots=survival (atrisk cb) outs=dataout;
  class subjid cmabl trt01pn(ref='1');
  time avisitn*event (1) = trt01pn cmabl;
run;
```

Proportion of subjects requiring rescue treatment (systemic corticosteroid for > 5 consecutive days) or surgery for nasal polyps during the 24-week Treatment Period will be calculated with the corresponding 95% CI by treatment group. Clopper-Pearson interval will be used to calculate the exact confidence interval for binomial proportion. The difference between each CBP-201 group and placebo group and the corresponding 95% CI will be calculated as well. Cochran–Mantel–Haenszel (CMH) test stratified by presence of comorbid asthma will be performed and odds ratio will be provided with 95% confidence interval.

The sample SAS code for CMH test:

```
proc freq data=data order=data;
  table trt01pn*rescuetrt*cmabl / relrisk cmh;
run;
```

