9.5.2 Secondary Analyses

Using the same models described in Section 10.3.1, the comparisons between the CBP-201 Q4W 300 mg group to the placebo group using a two-sided test at the alpha=0.05 level of significance. “Study success” for the Q4W group is defined as a statistically significant result for both of the co-primary endpoints.

However, if the primary analysis is not statistically significant for one or both of the two co-primary endpoints, the results from the secondary analysis will be exploratory rather than confirmatory.

The similar analyses to endoscopic NPS will be performed for each secondary continuous variable:

- Percentage of maxillary sinus volume occupied by disease on CT and Lund-Mackay Computed Tomography scores from patients enrolled at Study Sites that are approved and qualified to perform CT scans
- University of Pennsylvania Smell Identification Test (UPSIT)
- Visual analogue scale for rhinosinusitis (VAS-RS)
- Total nasal symptom score (TNSS)
- 22-item Sinonasal Outcome Test (SNOT-22)
- Average daily anterior rhinorrhea score
- Average daily posterior rhinorrhea score
- Average daily loss of smell score
- Daily subject-assessed nasal peak inspiratory flow (NPIF)

Proportion of patients requiring rescue treatment (systemic CS for > 5 consecutive days) or having had surgery for nasal polyps through Week 24 will be calculated with the corresponding 95% CI by treatment group. The difference between each CBP-201 group and placebo group and the corresponding 95% CI will be calculated as well. The Cochran-Mantel-Haenszel (CMH) test adjusted by comorbid asthma will be performed to compare the proportion between each CBP-201 group and placebo group.

The Kaplan-Meier plot will be presented for the time to rescue treatment (systemic CS for >5 consecutive days) or surgery for nasal polyps through Week 24. Median of the time and the corresponding 95% CI will be calculated for each treatment group. The event-free rate at Week 24 week will be presented with 95% CI. Log-rank test will be performed to compare the event free distribution between each CBP-201 group and placebo group.

All secondary analyses will be conducted using two-sided tests at the alpha=0.05 level of significance.

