9.5.3 Exploratory Analyses

Exploratory analyses will be done using a similar model to the primary endoscopic NPS endpoint analysis. Endpoints will include:

- Change from baseline at Week 24 in FEV1 for subjects with asthma
- Proportion of patients with minimal clinically important difference ≥ 8.9 in SNOT-22 at Week 24
- Change from baseline at Week 16 in endoscopic NPS
- Change from baseline at Week 16 in Average daily NCS
- Change from baseline at Week 24 in European quality of life scale (EQ 5D-5L)
- Healthcare resource utilization through Week 24

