#### 4.11.5 Exploratory Efficacy Analysis

Exploratory analyses will be done using a similar model to the primary endoscopic NPS endpoint analysis. Endpoints will include:

- Change from baseline at Week 24 in FEV1 for subjects with asthma
- Change from baseline at Week 16 in endoscopic NPS
- Change from baseline at Week 16 in Average daily NCS
- Change from baseline at Week 24 in European quality of life scale (EQ 5D-5L)

Weekly mean of daily nasal congestion score will be calculated as sum of non-missing daily nasal congestion score divided by number of days with non-missing daily nasal congestion score using analysis window (Table ).

Proportion of subjects with minimal clinically important difference  $\geq 8.9$  in SNOT-22 at Week 24 will be calculated with the corresponding 95% CI by treatment group. Clopper-Pearson interval will be used to calculate the exact confidence interval for binomial proportion. The difference between each CBP-201 group and placebo group and the corresponding 95% CI will be calculated as well. Cochran–Mantel–Haenszel (CMH) test stratified by presence of comorbid asthma will be performed and odds ratio will be provided with 95% confidence interval.

The sample SAS code for CMH test:

```
proc freq data=data order=data;
  table trt01pn*snot*cmabl / relrisk cmh;
run;
```

Healthcare resource utilization at each visit up to Week 24 will be summarized using descriptive statistics by treatment and overall, as described in 4.13.4.

By-subject listings of each exploratory efficacy endpoint will also be provided.

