#### **4.15 Changes in the Conduct of the Study or Planned Analysis**

Enrollment of Sponsor's Phase 2 trial evaluating CBP-201 in chronic rhinosinusitis with nasal polyps, which commenced in June 2021, has faced challenges due to the macroenvironment -- namely ongoing impact of COVID and the current Russia-Ukraine conflict throughout [Eastern] Europe.

Therefore, the Sponsor has made the decision to terminate this trial early, and the planned analyses have been changed to focus on safety assessments.

For the efficacy endpoints, only descriptive summary statistics will be provided for the co-primary efficacy assessments. No formal hypotheses will be tested due to the small sample size. No sensitivity or subgroup analyses will be performed. All other efficacy assessments will be listed except percentage of maxillary sinus volume occupied by disease on CT and Lund-Mackay Computed Tomography scores.

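### Do the sample CMH code lines in SAP 4.11.4 and 4.11.5, which stratify by treatment instead of asthma, need correcting?

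*SAP*

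**What the plan says.** SAP 4.11.4 covers the proportion of subjects needing rescue treatment or polyp surgery during the 24-week treatment period. It asks for each CBP-201 group to be compared with placebo and for a CMH "test stratified by presence of comorbid asthma will be performed and odds ratio will be provided with 95% confidence interval". The sample code directly below is "table trt01pn*rescuetrt*cmabl / relrisk cmh".

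SAP 4.11.5 uses the same method sentence for the proportion reaching the SNOT-22 threshold of 8.9, with the sample code "table trt01pn*snot*cmabl / relrisk cmh".

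Protocol 9.5.2 agrees with the SAP sentence for rescue or surgery: a CMH "test adjusted by comorbid asthma will be performed to compare the proportion between each CBP-201 group and placebo group". Protocol 9.5.3 names no CMH test for the SNOT-22 proportion and says only "Exploratory analyses will be done using a similar model to the primary endoscopic NPS endpoint analysis".

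SAP 4.15, added when the trial was stopped early, limits efficacy output to descriptive statistics for the co-primary endpoints. It states "No formal hypotheses will be tested due to the small sample size", and for the rest "All other efficacy assessments will be listed except percentage of maxillary sinus volume occupied by disease on CT" (Lund-Mackay scores are excepted too).

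**The concern.** Each code line contradicts the sentence it is meant to illustrate. With treatment first and asthma last, the test asks whether asthma predicts the outcome within arms. No part of either document asks that question. The comparison of CBP-201 with placebo drops out.

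The failure would also be silent. Outcome by asthma is a 2×2 table within every arm, so the procedure would return an ordinary-looking common odds ratio and p-value with no warning. Had these tests been run as printed and reported as treatment comparisons, a real benefit could have been missed, or an asthma association mistaken for a drug effect.

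**Working it through.** **Inputs.** The documents give no variable list. The MMRM text and code in SAP 4.11.2.1 show that `trt01pn` is treatment and `cmabl` is comorbid asthma. The imputation code in SAP 4.11.3.1 ("modelobs=(trt01pn='1", annotated as the control group) shows that placebo is coded 1. The documents give no rescue or SNOT-22 response rates, so every count below is an assumption. The plan states no figure to reproduce.

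**Step 1: reading the code.** In a PROC FREQ request A*B*C, A is the stratum and B×C is the table. As printed, the stratum is treatment and the table is outcome × asthma. As described in the prose, the stratum is asthma and the table is treatment × outcome.

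**Step 2: the two orders on an assumed table.** Take 24 patients with and 24 without asthma per arm (48 rather than the planned 49, so that the split is even). Let rescue events be 6+6 on placebo and 1+1 on Q2W. The Mantel-Haenszel odds ratio is Σ(ad/N) / Σ(bc/N).

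- Prose order, each asthma stratum with Q2W 1/23 and placebo 6/18: (1×18 + 1×18) / (23×6 + 23×6) = 36/276 = 0.130.
- Its chi-square: observed 2; expected 2 × (24×7/48) = 7; variance 2 × 24×24×7×41/(48²×47) = 3.053; (2−7)²/3.053 = 8.19, p = 0.004. The Robins-Breslow-Greenland 95% CI is 0.03 to 0.62.
- Printed order, placebo stratum 6,6 over 18,18 and Q2W stratum 1,1 over 23,23: (6×18 + 1×23) / (6×18 + 1×23) = 1.00, p = 1.00.

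**Step 3: is 1.00 forced by the even split?** Yes, so vary it. Let events without + with asthma be 4+8 on placebo and 1+2 on Q2W.

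- Prose order: (1×20 + 2×16) / (23×4 + 22×8) = 52/268 = 0.194.
- Exchange the two arms' counts: 268/52 = 5.15.
- Printed order: (8×20 + 2×23) / (4×16 + 1×22) = 206/86 = 2.40, p = 0.15, both before and after the exchange.

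The printed statistic is a sum over treatment strata, so relabelling the arms cannot alter it. That holds for any counts.

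**Step 4: rejection rates.** Simulation with 49 per arm, 20,000 runs, assumed event rates, two-sided 0.05; the prose-order test compares Q2W with placebo:

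| Scenario | Prose order | Printed order |
|---|---|---|
| Placebo 30%, Q2W 10%, Q4W 15%; no asthma effect | 71.1% | 5.0% |
| Placebo 45%, Q2W 15%, Q4W 25%; no asthma effect | 91.9% | 5.2% |
| No treatment effect; asthma 30%, no asthma 10% | 5.1% | 87.9% |

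**Step 5: which planned outputs depend on these lines?**

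| SAP section | Endpoint | Test in the prose | Sample code | Output after SAP 4.15 |
|---|---|---|---|---|
| 4.11.4 | Rescue or surgery | CMH, asthma strata | Wrong order | Listing only |
| 4.11.5 | SNOT-22 response | CMH, asthma strata | Wrong order | Listing only |
| 4.12.3 | Adverse events of special interest | CMH, asthma strata, if at least 4 subjects in any arm | None | Safety summary, still planned |

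The two wrong lines sit in the two rows where no test is performed. The row where a test may still be run is specified correctly.

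**The case for a change.** The best case for a correction is that it costs two lines and the error is beyond dispute. SAP section 1 says the document outlines programming specifications, and 4.11.4 and 4.11.5 still print the code with no note that it is withdrawn. They hold the SAP's only CMH examples, and SAP 4.12.3 still calls for an asthma-stratified CMH test without code of its own. A programmer could copy the wrong pattern into a live safety table.

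The description of the error stands in full, and so does the point that it would not announce itself. The argument from reuse is weaker:

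- SAP 4.15 is itself the withdrawal. It overrides the MMRM, imputation, Cox and subgroup sections in the same way, and none of those is annotated either.
- The lines are offered as samples, and the method sentence above each is unambiguous. Other samples are loose too: the Cox code in 4.11.4 omits the baseline NPS and NCS covariates that its prose requires. A competent programmer works from the prose, and SAP 4.1 has a biostatistician check every table independently.
- SAP 4.12.3 asks for a risk difference with its confidence interval and a p-value. The efficacy lines request odds ratios and relative risks, so they could not be lifted across unchanged. Anyone rewriting them would have the correct stratification in front of them.

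One limit on the charge itself: the conflict with the protocol concerns rescue or surgery only. For SNOT-22 response the conflict is inside the SAP, between its sentence and its code.

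**Conclusion.** This is a clerical slip in sample code for two tests that the plan no longer performs. The code is wrong and the SAP sentences state the intended test, supported for rescue or surgery by Protocol 9.5.2. Correcting the lines would change no planned table, estimate, p-value or conclusion, so there is nothing to gain from a change to the plan.

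The conclusion rests on SAP 4.15 remaining in force. The odds ratios and rejection rates above rest on assumed event counts and rates; they show what the printed order would have done in the full-size trial, not what will happen in this one. If the efficacy tests were ever reinstated, the prose already tells the analyst what to run: asthma as the stratum, one CBP-201 arm against placebo at a time.
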